7.2. Participant Discontinuation/Withdrawal from the Study

Every attempt should be made to keep participants in the study irrespective of their adherence to treatment with study intervention in order to minimize the amount of missing data and to enable assessment of study objectives as planned by the study protocol.

A participant may withdraw from the study:

- at any time at his/her own request
- at the request of his/her designee (for example, parents or legal guardian)
- at the discretion of the investigator for safety, behavioral, compliance, or administrative reasons
- if the participant becomes pregnant during the study
- if enrollment in any other clinical study involving an investigational product or enrollment in any other type of medical research judged not to be scientifically or medically compatible with this study
- if the participant, for any reason, requires treatment with another therapeutic agent that has been demonstrated to be effective for treatment of the study indication, discontinuation from the study occurs prior to introduction of the new agent.

At the time of discontinuing from the study, if possible, an early termination visit should be conducted, as shown in the SoA. See SoA for data to be collected at the time of study discontinuation and follow-up and for any further evaluations that need to be completed. The participant will be permanently discontinued both from the study intervention and from the study at that time.

If the participant withdraws consent for disclosure of future information, the sponsor may retain and continue to use any data collected before such a withdrawal of consent. If a participant withdraws from the study, he/she may request destruction of any samples taken and not tested, and the investigator must document this in the site study records.

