6.5. Concomitant Therapy

In this study, participants taking DPP-4i are required to stop DPP-4i treatment at randomization. In case of weekly DPP-4i, it must be stopped 1 week before randomization. Participants taking other OAMs are required to continue the same dose of OAM during the study period; however, OAM dose modifications are allowed in the event of hypoglycemia.

Participants will be permitted to use concomitant medications that they require during the study, except certain medications that may interfere with the assessment of efficacy and safety characteristics of the study intervention (Section [5.2](#)).

Prohibited medications include

- Any other antihyperglycemic medications, except for study-specified permitted concomitant OAMs
- Any medications that promote weight loss (e.g., Sanorex® [mazindol])
- Any chronic (>2 weeks or 14 days) systemic glucocorticoid therapy (excluding topical, intra-ocular, intranasal, or inhaled preparations)

Short-term insulin use is allowed for certain clinical situations (e.g., elective surgery, during hospitalization, hyperosmolar states). Rescue therapy with insulins will be also allowed in certain situations after randomization due to severe, persistent hyperglycemia (see Section [6.5.1](#)). If insulin is prescribed as a rescue therapy, it must be differentiated from short-term use of insulin therapy for medical emergencies when reported in the eCRF. After early discontinuation of study intervention, any antihyperglycemic medications, except for GLP-1 receptor agonists may be allowed.

Investigative site staff will inform participants that they must consult with the investigator or a designated site staff member upon being prescribed any new medications during the study. This may not be possible when initiated for treatment of medical emergencies, in which case the participant will inform the investigator or a designated site staff member as soon as possible.

Nonstudy medications taken by participants who are screened but not randomized will not be reported to Lilly unless an SAE or AE occurs that the investigator believes may have been caused by a study procedure.

Any medication or vaccine (including over-the-counter [OTC] or prescription medicines, vitamins, and/or herbal supplements) or other specific categories of interest that the participant is receiving at the time of enrollment or receives during the study must be recorded along with:

- Reason for use

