6.5.1. Management of Participants with Severe, Persistent Hyperglycemia

Add-on glycemic rescue therapy with insulin will be allowed for participants who meet any of the following prespecified criteria for severe, persistent hyperglycemia. In this case, the investigator determines if a new intervention is warranted, after noncompliance with the assigned therapeutic regimen is ruled out as the reason for hyperglycemia. Participants should continue administering assigned study intervention. Glycemic rescue therapy by adding other OAM and increasing dose of study-specified concomitant OAM will not be allowed.

The criteria are as follows:

- a) Blood glucose concentration measured by weekly 1-point SMBG before breakfast
>270 mg/dL (>15.0 mmol/L) over at least a consecutive 2-week period any time during the first 8 weeks post-randomization;
OR
- b) Blood glucose concentration measured by weekly 1-point SMBG before breakfast
>240 mg/dL (>13.3 mmol/L) over at least a consecutive 2-week period at any time 9 to 26 weeks post-randomization;
OR
- c) Blood glucose concentration measured by weekly 1-point SMBG before breakfast
>200 mg/dL (>11.1 mmol/L) over a consecutive 2-week period at any time 27 to 52 weeks post-randomization.

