7.1. Discontinuation of Study Intervention

In rare instances, it may be necessary for a participant to permanently discontinue (definitive discontinuation) study intervention. If study intervention is definitively discontinued, the participant will remain in the study to be evaluated for all planned efficacy and safety measurements. See the SoA (Section 1.3) for data to be collected at the time of discontinuation of study intervention and follow-up and for any further evaluations that need to be completed.

Possible reasons leading to permanent discontinuation of study intervention include:

Participant Decision

The participant requests to discontinue study intervention.

Discontinuation due to a hepatic event or liver test abnormality.

Participants who are discontinued from study intervention due to a hepatic event or liver test abnormality should have additional hepatic safety data collected via the eCRF (Section 10.5, Appendix 5). Discontinuation of the study intervention for abnormal liver tests **should be** considered by the investigator when a participant meets 1 of the following conditions after consultation with the Lilly's CRP or CRS:

- ALT or aspartate aminotransferase (AST) >8X upper limit of normal (ULN)
- ALT or AST >5X ULN for more than 2 weeks
- ALT or AST >3X ULN and total bilirubin level (TBL) >2X ULN or international normalized ratio (INR) >1.5
- ALT or AST >3X ULN with the appearance of fatigue, nausea, vomiting, right upper-quadrant pain or tenderness, fever, rash, and/or eosinophilia (>5%)
- Alkaline phosphatase (ALP) >3X ULN
- ALP >2.5X ULN and TBL >2X ULN
- ALP >2.5X ULN with the appearance of fatigue, nausea, vomiting, right quadrant pain or tenderness, fever, rash, and/or eosinophilia (>5%)

Additional circumstances in which participants will be discontinued from the study intervention include:

A participant will be discontinued from study intervention due to any of the following:

- If a participant is inadvertently enrolled and it is determined that continued study intervention would not be medically appropriate (See Section 7.2.1)
- If a participant misses 3 continuous injections
- Acute or chronic pancreatitis

- If a participant is diagnosed with an active or untreated malignancy (other than basal or squamous cell skin cancer, in situ carcinomas of the cervix, or in situ prostate cancer) after randomization
- If a participant is diagnosed with C-cell hyperplasia or medullary thyroid carcinoma (MTC) after randomization

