- Any other treatment-emergent AE (TEAE), SAE, or clinically significant laboratory value for which the investigator believes that permanent study intervention discontinuation is the appropriate measure to be taken
- Any significant study intervention-related hypersensitivity reaction;
- If any other antihyperglycemic medications except for study-specified concomitant OAMs and insulin is initiated, and the participant refuses to discontinue these medications
- If female participant becomes pregnant (Section 7.2)
- If a participant is diagnosed with T1D
- If an investigator, site personnel performing assessments, or participant is unblinded
- if the participant or the participant's designee, for example, legal guardian, requests that the participant be withdrawn from study intervention
- If the investigator or sponsor decides that the participant should be withdrawn from study intervention; if the investigator decides to permanently discontinue study intervention because of an SAE or a clinically significant laboratory value, Lilly or its designee should be alerted immediately.

Participants who discontinue the study intervention permanently will receive another glucose-lowering intervention (Section 6.5) and will continue participating in the study according to the protocol to collect all planned efficacy and safety measurements.

See the SoA for data to be collected at the time of intervention discontinuation and follow-up and for any further evaluations that need to be completed.

7.1.1. **Temporary Discontinuation**

In certain situations, after randomization, the investigator may need to temporarily discontinue (interrupt) study intervention (for example, due to an AE or a clinically significant laboratory value). If study intervention interruption is due to an AE, the event is to be documented and followed according to the procedures in Section 10.3 of this protocol. Every effort should be made by the investigator to maintain participants on study intervention and to restart study intervention after any temporary interruption, as soon as it is safe to do so.

Investigators should inform the Sponsor that study intervention has been temporarily interrupted. The data related to temporary interruption of study intervention will be documented in source documents and entered in the eCRF.

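### The last bullet of Protocol 7.2, read literally, takes participants out of the study before another diabetes drug starts, while 7.1, 8.3.3, 6.5 and 6.5.1 keep them in; a site that follows it loses planned safety follow-up

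*Protocol*

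**What the plan says.** Protocol 7.2 opens with the aim of keeping participants in the study whatever their adherence, then lists situations in which a participant may withdraw. The last is a participant who, whatever the reason, needs another agent shown to work in the study indication: "discontinuation from the study occurs prior to introduction of the new agent". The next paragraph asks for an early termination (ET) visit if possible and adds: "The participant will be permanently discontinued both from the study intervention and from the study at that time".

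Other sections deal with the same participants:

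- **6.5.1** allows add-on insulin for severe, persistent hyperglycemia: "Participants should continue administering assigned study intervention".
- **6.5** allows short-term insulin in certain clinical situations, and also says: "After early discontinuation of study intervention, any antihyperglycemic medications, except for GLP-1 receptor agonists may be allowed".
- **7.1** says that if study drug is stopped for good, "the participant will remain in the study to be evaluated for all planned efficacy and safety measurements". Such participants "will receive another glucose-lowering intervention (Section 6.5) and will continue participating in the study according to the protocol". One listed reason for stopping study drug is: "If any other antihyperglycemic medications except for study-specified concomitant OAMs and insulin is initiated, and the participant refuses to discontinue these medications".
- **8.3.3**, under hypersensitivity, gives other glucose-lowering treatment after permanent discontinuation and keeps the participant in the study.

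Protocol 9.3 defines the safety sets SS1 and SS2 to hold data regardless of adherence or rescue. Section 9.4.4 uses both for the safety analyses unless otherwise stated.

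**The concern.** A site with a participant who needs rescue insulin, or replacement therapy after stopping study drug, finds two incompatible instructions. One keeps the participant under observation to Week 52 and Visit 801. The other ends participation before the new drug is given.

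Safety data are at stake. Under the 7.2 bullet, new adverse events after Visit 801 and the remaining scheduled laboratory, vital-sign and ECG measurements are not collected, although SS1 and SS2 are defined to include them. The people removed are not a random subset: they are those with poor glycemic control or those who came off study drug. Data not collected cannot be recovered at analysis.

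**Working it through.** **1. Do the passages really conflict?** The bullet's trigger is need for another effective agent, whatever the reason. Insulin fits: 6.5.1 uses it as glycemic rescue, and 2.1 cites insulin glargine as a comparator in type 2 diabetes.

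| Situation | 7.2, last bullet | Other section |
|---|---|---|
| Rescue insulin | Leaves study before insulin | 6.5.1: insulin added, study drug continues (staying in is implied) |
| Short-term insulin | Leaves study before insulin | 6.5: allowed (staying in is implied) |
| Replacement drug after stopping study drug | Leaves study before the drug | 7.1: drug given, stays for all planned measurements (explicit); 8.3.3 the same for hypersensitivity; 6.5 permits the drug |
| Prohibited drug started, participant refuses to stop it | Leaves study | 7.1: comes off study drug, stays in the study (explicit) |

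The explicit conflict is with 7.1, and with 8.3.3 for hypersensitivity. The conflict with 6.5 and 6.5.1 is by clear implication.

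**2. Follow-up lost per participant.** Inputs: planned observation runs to Week 56 (Schedule of Activities); after study exit there is an ET visit and then Visit 801 about 4 weeks later (4.1). For exit at Week w with Visit 801 attended:

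Loss = 56 − (w + 4) = 52 − w weeks.

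- w = 8: 44 weeks
- w = 16: 36 weeks
- w = 26: 26 weeks
- w = 38: 14 weeks

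If Visit 801 is not done, 4.1 makes the ET visit the last one and the loss is 56 − w.

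By 6.5.1 rescue window: criterion (a) must hold "over at least a consecutive 2-week period any time during the first 8 weeks post-randomization", so w runs from 2 to 8 and the loss from 50 to 44 weeks. If the 2-week run must also fall inside windows (b) and (c), the earliest weeks are 9 + 2 = 11 and 27 + 2 = 29. The losses are then 41 to 26 weeks and 23 to 0 weeks. If a run may begin before its window opens, the upper ends are at most 52 − 9 = 43 and 52 − 27 = 25.

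**3. Scheduled measurements lost.** From the Schedule of Activities:

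- Laboratory and ECG after baseline: Weeks 26 and 52, ET and Visit 801. Exit before Week 26 loses both treatment-period points; exit between Weeks 26 and 52 loses one.
- Vital signs after baseline: Weeks 8, 16, 26, 38 and 52, and ET, with no mark at Visit 801. Exit before Week 8 loses five scheduled visits; between Weeks 8 and 16, four; between 16 and 26, three; between 26 and 38, two; between 38 and 52, one. A single ET measurement stands in.

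The ET visit is not a full substitute. For variables not collected at every visit, SAP 4.1 excludes ET data off the collection schedule from the MMRM. An ET laboratory value taken before Week 26 therefore stays out of the 52-week laboratory MMRM, though it can still serve shift and LOCF analyses.

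**4. Study level.** The documents give no rescue or discontinuation rate and no way to know how many sites would follow the bullet. As an assumption only: if 2%, 5% or 10% of 585 participants (about 12, 29 or 59) left at Week 26, the loss is 585 × share × 26 ≈ 304, 760 or 1,521 participant-weeks. Against 585 × 56 = 32,760 planned, that is 0.9%, 2.3% or 4.6%. For exit weeks from 38 back to 8 and the same shares, the range is 0.5% to 7.9%.

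**5. Primary analysis.** The plan's power reproduces. With 352 and 176 evaluable, SE = √(1/176 + 1/352) = 0.0923 and 0.3/0.0923 = 3.25, so power is 90.1% (90.0% by the noncentral t). The bullet hardly touches this: EAS1 already excludes data after rescue or after stopping study drug.

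**The case against.** The best defense is context. The list in 7.2 is permissive, and 7.2 and 4.1 both open with retention. The specific instructions in 6.5.1 and 7.1 should govern the specific situations. The rest of the plan assumes retention: rescue details go on an eCRF (8.3.3), the SAP plans rescue-insulin tables, and SS1 and SS2 are defined regardless of rescue. A site also has to open 6.5.1 to find the rescue thresholds, and there it reads that study drug continues.

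Much of this stands as an argument that many sites would do the right thing, and that rescued participants are the least likely to be removed by mistake. It does not remove the conflict. The bullet carries its own declarative instruction on timing, and neither the stem nor the retention aim exempts rescue or replacement therapy.

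A reader might infer that the bullet is wrong for every participant. The documents do not go that far: 6.5 withholds GLP-1 receptor agonists after study drug stops, so someone who then needs one has no stated in-study route, and the bullet has an arguable role there.

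A reader might also infer that all later safety information is lost. It is not. SAEs and adverse events of special interest already reported are followed up (8.3), SAEs the investigator learns of after exit are still reported (8.3.1), and the hypoglycemia summaries already exclude data after another antihyperglycemic (9.4.4).

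**Conclusion.** The point holds as an internal contradiction: the bullet is wrong as written for participants on rescue insulin, short-term insulin or replacement therapy permitted by 6.5, and for those whom 7.1 takes off study drug for refusing to stop a prohibited drug.

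Where it is followed, about 52 − w weeks of planned SS2 observation are lost per participant leaving at Week w, plus both treatment-period laboratory and ECG points if exit is before Week 26. This assumes that Visit 801 is attended about 4 weeks after the ET visit. The study-level loss cannot be derived: it depends on site behavior and on rates the documents do not give, and 7.1 calls permanent discontinuation of study drug rare.

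A reader might infer that the primary result or its power is at risk, or that retaining these participants would test the missing-at-random assumption of the primary MMRM. Neither follows. EAS1 already leaves these data out. An HbA1c analysis of all values regardless of rescue or discontinuation would target a treatment-policy effect; it would not check missing at random for the hypothetical estimand. The consequence is confined to safety follow-up.

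**What to change.** Delete the last bullet of 7.2, or limit it so that it no longer reaches therapy the protocol permits. State in its place that:

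- starting rescue insulin under 6.5.1, short-term insulin under 6.5, or another antihyperglycemic that 6.5 permits after study drug stops is not in itself a reason to leave the study;
- a participant who starts a prohibited antihyperglycemic and refuses to stop it comes off study drug under 7.1 but stays in follow-up;
- all these participants continue through Visit 9 and Visit 801.

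Keep the 6.5 restriction on GLP-1 receptor agonists. Wording that covered any antihyperglycemic without this limit would create a new conflict with 6.5.

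The cost is a small protocol amendment with IRB/IEC approval (10.1.1). No visit, assessment or analysis is added, because 7.1 already expects these participants to be followed.

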7.2.1. Discontinuation of Inadvertently Enrolled Participants

If the sponsor or investigator identifies a participant who did not meet enrollment criteria and was inadvertently enrolled, then the participant should be discontinued from study intervention unless there are extenuating circumstances that make it medically necessary for the participant to continue on study intervention. If the investigator and the sponsor CRP or CRS agree it is medically appropriate to continue, the investigator must obtain documented approval from the sponsor CRP or CRS to allow the inadvertently enrolled participant to continue in the study with or without treatment with study intervention. Safety follow-up should be performed as outlined in Section 1.3 (SoA), Section 8.2 (Safety Assessments), and Section 8.3 (Adverse Events and Serious Adverse Events) of the protocol.

7.3. Lost to Follow-up

A participant will be considered lost to follow-up if he or she repeatedly fails to return for scheduled visits and is unable to be contacted by the study site. Site personnel or designee are expected to make diligent attempts to contact participants who fail to return for a scheduled visit or were otherwise unable to be followed up by the site.

8. Study Assessments and Procedures

- Study procedures and their timing are summarized in the SoA (Section 1.3.)
- Immediate safety concerns should be discussed with the sponsor immediately upon occurrence or awareness to determine if the participant should continue or discontinue study intervention.
- Adherence to the study design requirements, including those specified in the SoA, is essential and required for study conduct.
- All screening evaluations must be completed and reviewed to confirm that potential participants meet all eligibility criteria. The investigator will maintain a screening log to record details of all participants screened and to confirm eligibility or record reasons for screening failure, as applicable.

8.1. Efficacy Assessments

8.1.1. Primary Efficacy Assessments

The primary efficacy measure will be evaluated at 26 weeks:

- Change from baseline in HbA1c.

8.1.2. Secondary Efficacy Assessments

The following secondary efficacy measures will be evaluated through 26 and 52 weeks:

- Change from baseline in HbA1c.
- Proportion of participants achieving HbA1c target of $\leq 6.5\%$ and $< 7.0\%$;
- Change from baseline in FSG ;
- Change from baseline in 6-point SMBG;
- Change from baseline in body weight;

8.2. Safety Assessments

Planned time points for all safety assessments are provided in the SoA (Section 1.3).

8.2.1. Physical Examinations

- A complete physical examination will include, at a minimum, assessments of the Cardiovascular, Respiratory, Gastrointestinal and Neurological systems. Height and weight will also be measured and recorded, per Section 1.3.
- A brief physical examination will include, at a minimum, assessments of the skin, lungs, cardiovascular system, thyroid exam, and abdomen (liver and spleen).
- Investigators should pay special attention to clinical signs related to previous serious illnesses.

8.2.2. Vital Signs

For each participant, vital sign measurements should be conducted according to the SoA (Section 1.3).

- The participant should sit quietly for 5 minutes before vital sign measurements are taken. For each parameter, 2 measurements will be taken using the same arm; the recordings should be taken at least 1 minute apart. Blood pressure (BP) can be measured by either an automated or semi-automated blood pressure machine, but the same machine must be used during study period.
- Vital sign measurements should be taken before obtaining an electrocardiogram (ECG) tracing and before collection of blood samples for laboratory testing, at visits where required.

